9.2.2.3 Physical Examination

Targeted post-transplant physical examinations will also include vital signs (systolic and diastolic blood pressure, pulse rate, respiratory rate, and temperature) and aGVHD assessments. The aGVHD assessment will be assessed using established staging criteria (see Appendix F: Graft-versus-host-disease scales). Overall grading and response to GVHD therapy will be measured through the use of the consensus and IBMTR GVHD severity indices. GVHD assessments will be performed at screening and Days +60 & +90. If lenalidomide is initiated, GVHD assessments will be performed weekly during scheduled

visits and continuing until 30 days after the last dose of lenalidomide. GVHD assessments will also be documented at Day +60 and Day +120 after the initiation of lenalidomide

10. ADVERSE EVENTS

10.1 Definitions

10.1.1 Adverse Event (AE)

The term “adverse event” covers any sign, symptom, syndrome, or illness that appears or worsens in a subject during the period of observation in the clinical study and that may impair the wellbeing of the subject. The term also covers laboratory findings or results of other diagnostic procedures that are considered to be clinically significant (*e.g.*, that requires unscheduled diagnostic procedures or treatment measures, or result in withdrawal from the study).

The adverse event may be:

- A new illness/condition;
- Worsening of a sign or symptom of the condition under treatment, or of a concomitant illness/condition;
- An effect of the study drug; or
- A combination of 2 or more of these factors.

No causal relationship with the study drug or with the clinical study itself is implied by the use of the term “adverse event.”

Surgical procedures themselves are not adverse events; they are therapeutic measures for conditions that require surgery. The condition(s) for which the surgery is required may be an adverse event. Planned surgical measures permitted by the clinical study protocol and the condition(s) leading to these measures are not adverse events.

When a clear diagnosis is available that explains the abnormal objective findings, this diagnosis will be recorded as an adverse event and not the abnormal objective findings (*e.g.*, viral hepatitis will be recorded as the adverse event and not the transaminase elevation). If a definitive diagnosis is not available, then the sign(s) (*e.g.*, clinically significant elevation of transaminase levels) or symptom(s) (*e.g.*, abdominal pain) will be recorded as the adverse event.

Adverse events fall into the categories “serious” and “nonserious.”

10.1.2 Serious Adverse Event (SAE)

A serious adverse event is one that at any dose of the study drug or at any time during the period of observation:

- Results in death;
- Is life-threatening;
- Requires inpatient hospitalization or prolongation of existing hospitalization;
- Results in persistent or significant disability/incapacity;
- Is a congenital anomaly/birth defect; or
- Is medically important.

Life-threatening means the subject was at immediate risk of death at the time of the serious adverse event; it does not refer to a serious adverse event that hypothetically might have caused death if it were more severe.

Persistent or significant disability or incapacity means there is a substantial disruption of a person's ability to carry out normal life functions.

Medical and scientific judgment should be exercised in deciding whether other adverse events may be considered serious because they jeopardize the subject or may require intervention to prevent one of the other outcomes listed in the definition above. Examples of such events are: intensive treatment in an emergency room or at home for allergic bronchospasm, blood dyscrasias, or convulsions that do not result in hospitalization; or development of drug dependency or drug abuse. "Medically important" should be marked only if no other serious criteria are met.

An "unexpected SAE" is any SAE for which the nature, specificity or severity is not consistent with the current Revlimid Investigator Brochure or in other risk information that has been given to the Investigator.

Clarification of the difference in meaning between "severe" and "serious"

The term "severe" is often used to describe the intensity (severity) of a specific event (as in mild, moderate, or severe myocardial infarction); the event itself, however, may be of relatively minor medical significance (such as severe headache). This is not the same as "serious," which is based on the outcome or action criteria usually associated with events that pose a threat to life or functioning. Seriousness (not severity) serves as a guide for defining regulatory reporting obligations.

10.1.3 Events not considered to be SAEs are hospitalizations for:

- A standard procedure for protocol therapy administration. However, hospitalization or prolonged hospitalization for a complication of therapy administration will be reported as an SAE.
- Routine treatment or monitoring of the studied indication not associated with any deterioration in condition.
- The administration of blood or platelet transfusion as routine treatment of studied Indication. However, hospitalization or prolonged hospitalization for a complication of such transfusion remains a reportable SAE.
- A procedure for protocol/disease-related investigations (*e.g.*, surgery, scans, endoscopy, sampling for laboratory tests, bone marrow sampling). However, hospitalization or prolonged hospitalization for a complication of such procedures remains a reportable SAE.
- Hospitalization or prolongation of hospitalization for technical, practical, or social reasons, in absence of an AE.
- A procedure that is planned (*i.e.*, planned prior to starting of treatment on study); must be documented in the source document and the CRF. Hospitalization or prolonged hospitalization for a complication remains a reportable SAE.
- An elective treatment of or an elective procedure for a pre-existing condition unrelated to the studied indication.

- Emergency outpatient treatment or observation that does not result in admission, unless fulfilling other seriousness criteria above.

If an AE is considered serious, both the AE CRF and the SAE Report Form must be completed. For each SAE, the Investigator will provide information on severity, start and stop dates, relationship to investigational product (IP), action taken regarding IP, and outcome.

10.1.4 Non-Serious Adverse Event

A non-serious adverse event is any adverse event not meeting any of the serious adverse event criteria.

10.1.5 Abnormal Laboratory Values

The investigator must appraise all abnormal laboratory results for their clinical significance. If any abnormal laboratory result is considered clinically significant, the investigator must provide details about the action taken with respect to the test drug and about the patient's outcome.

An abnormal laboratory value is considered to be an AE if the abnormality:

- Results in discontinuation from the study;
- Requires treatment, modification/ interruption of IP dose, or any other therapeutic intervention;
- Or is judged to be of significant clinical importance.

Regardless of severity grade, only laboratory abnormalities that fulfill a seriousness criterion need to be documented as a SAE. If a laboratory abnormality is one component of a diagnosis or syndrome, then only the diagnosis or syndrome should be recorded on the AE CRF. If the abnormality was not a part of a diagnosis or syndrome, then the laboratory abnormality should be recorded as the AE. If possible, the laboratory abnormality should be recorded as a medical term and not simply as an abnormal laboratory result (*e.g.*, record thrombocytopenia rather than decreased platelets).

10.2 Period of Observation

For the purpose of this study, the period of observation for adverse events starts on the day the subject signs informed consent. For subjects who fail screening, the period of observation ends on the date of screening failure. Treated subjects, including those who were prematurely discontinued from the study, will be followed for any adverse events that occur during the study from the time the subject signs the informed consent form until 28 days (\pm 2 days) following the last dose of study treatment (*i.e.*, the Follow-up Visit). However, if another course of anti-cancer therapy is initiated prior to the 28-day follow-up period visit, collection of adverse events will no longer be performed, with the exception of events that may be possibly, probably, or definitely related to the investigational agent or are clinically significant.

10.3 Documenting and Reporting of Adverse Events by the Investigator

Prior to initiation of the investigational agent, lenalidomide, only serious and non-serious adverse events deemed to be related or possibly related to study interventions will be

recorded and reported as adverse events for the study. Adverse events will be collected at each clinic visit based on observation and spontaneous reporting.

Once lenalidomide is initiated, all adverse events that occur must be documented in the case report form.

Toxicity will be scored using CTCAE Version 4.0 for toxicity and adverse event reporting. A copy of the CTCAE Version 4.0 can be downloaded from the CTEP homepage (http://ctep.cancer.gov/protocolDevelopment/electronic_applications/ctc.htm#ctc_40). All appropriate treatment areas should have access to a copy of the CTCAE Version 4.03. All adverse clinical experiences, whether observed by the investigator or reported by the patient, must be recorded, with details about the duration and intensity of each episode, the action taken with respect to the test drug, and the patient's outcome. The investigator must evaluate each adverse experience for its relationship to the test drug and for its seriousness.

The following approach will be taken for documentation and reporting:

- All adverse events (whether serious or nonserious) must be documented on the "Adverse Event" page of the case report form.
- For adverse events classified as serious (see Section 10.1.2) the Investigator must complete the "Serious Adverse Event" form at the time the SAE is detected. This form must be faxed to Celgene Drug Safety within 24 hours of discovery. All SAE's must also be reported to the IRB and DISC in accordance with the institution's policy. Serious and unexpected AE's must be reported to the appropriate regulatory agencies (e.g., FDA) by the sponsor to comply with regulatory requirements in accordance with 21 CFR parts 56 and 312.

Every attempt should be made to describe the adverse event in terms of a diagnosis that encompasses the component signs and symptoms. If only nonspecific signs or symptoms are present, then these should be recorded as separate diagnoses on the pages of the case report form.

All subjects who have adverse events, whether considered associated with the use of study drug or not, must be monitored to determine the outcome. The clinical course of the adverse event will be followed according to accepted standards of medical practice, even after the end of the period of observation, until a satisfactory explanation is found or the Principal Investigator considers it medically justifiable to terminate follow-up. Should the adverse event result in death, a full pathologist's report should be supplied, if possible.

10.3.1 Assessment of Causal Relationship of Study Drug

The Investigator will provide an assessment of the potential causal relationship between adverse events and study medication by determining whether or not there is a reasonable possibility that the event was caused by the study medication. The relationship or association of the adverse event to the study medication will be characterized as not related, probably not related, possibly related, probably related, or related:

Not Related: There is not a temporal relationship to the study drug administration or the adverse event is clearly due only to the progression of the underlying disease state, intercurrent illness, concomitant medication, concurrent therapy or other known cause.

Unlikely Related: There is little or no chance that the study drug administration caused the adverse event; the event is most likely due to another competing cause, including intercurrent illness, progression or expression of the disease state, or a reaction to a concomitant medication or concurrent therapy appearing to explain the reported adverse event.

Possibly Related: The association of the adverse event with the study drug administration is unknown; however, the adverse event is not reasonably attributed to any other condition.

Probably Related: When a reasonable temporal relationship exists between the adverse event and the study drug administration; significant symptoms abate upon discontinuation of the study drug and there is a reasonable explanation based on known characteristics of the study drug and there is no clear association with preexisting disease or therapy, intercurrent illness, concurrent therapy or other factor(s).

Related: When the adverse event is a known side effect of the study drug or there is a temporal relationship to the administration of the study drug; or the adverse event reappears upon re-administration of the study drug (rechallenge); or the significant symptoms of the adverse event abate upon discontinuation of the study drug (dechallenge).

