4.3 Dose Limiting Toxicity

DLT will be defined as any of the following adverse events that are not clearly unrelated to drug administration or treatment-emergent from lenalidomide and constitute a change from baseline irrespective of outcome. For the purpose of dose-escalation decisions and MTD determination, only DLTs that occur before 14 days after the last dose of lenalidomide administration will be taken into account.

1. Grade 3 or greater nausea, diarrhea, or vomiting despite the use of maximal medical intervention;
2. Grade 3 or greater acute GVHD despite the use of maximal medical intervention;
3. Any other clinically significant nonhematologic toxicity of grade 3 or greater considered not related to the underlying disease or intercurrent illness;
4. Grade 3 or greater neutropenia
5. Grade 4 thrombocytopenia or platelet count ≤ 50 thou/mm³ by day 28 of lenalidomide administration; or
6. Any treatment-related effect leading to a subject missing 3 or more doses of lenalidomide.

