10.4 Immediately Reportable Events

10.4.1 Serious Adverse Events

Serious adverse events (SAE) are defined above. The investigator must inform Celgene in writing using a Celgene SAE form or MEDWATCH 3500A form of any SAE within 24 hours of being aware of the event. The written report must be completed and supplied to Celgene by facsimile within 24 hours/1 business day. All SAE's must also be reported to the IRB and DISC in accordance with the institution's policy per 21 CFR 56.

The initial report must be as complete as possible, including an assessment of the causal relationship between the event and the investigational product(s). Information not available at the time of the initial report (*e.g.*, an end date for the adverse event or laboratory values received after the report) must be documented on a follow-up report. A final report to document resolution of the SAE is required. The Celgene tracking number RV-CL-AML-PI-002987 and the institutional protocol number should be included on SAE reports (or on the fax cover letter) sent to Celgene. A copy of the fax transmission confirmation of the SAE report to Celgene should be attached to the SAE and retained with the patient records.

Serious and unexpected AEs that are at least possibly related to the study drug must be reported to the FDA in accordance with 21CFR 312.32 IND Safety Reports.

Celgene Drug Safety Contact Information:

Celgene Corporation

Global Drug Safety and Risk Management

[name]

[name]

[name]

[contact]

E-mail: [contact]

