13.3 Analysis Methods

13.3.1 Safety

Safety evaluation will include monitoring for adverse events, scheduled laboratory assessments, vital sign measurements, and physical examinations. The intensity of adverse changes in physical signs or symptoms will be graded according to the CTCAE version 4. For all other adverse events not listed in the CTCAE, the intensity of these events will be assessed by the Investigator using a 5-point scale as described in Section 10.3.2.

The number of adverse events and the incidence of adverse events will be summarized. Adverse events will be summarized by maximum intensity (as described in Section 10.3.2) and relationship to study drug for each treatment group. Separate summaries will be provided for all adverse events, serious adverse events, treatment-related adverse events, and other significant adverse events (*e.g.*, adverse events leading to study discontinuation).

Clinical laboratory results will be listed by subject or, as appropriate, summarized descriptively by treatment group, which will include a display of change from baseline. Laboratory values outside of the normal ranges will be identified. Clinically significant hematologic laboratory abnormalities (*i.e.*, meet Grade 3, 4, or 5 criteria according to CTCAE v.4) will be listed and summarized.

Physical examination, vital sign, and GVHD data will be listed for each subject at each study visit. If appropriate, descriptive statistics for vital signs, both observed values and changes from baseline, will be summarized by treatment group.

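### The causality scale in Section 10.3.1 is neither ordered nor mutually exclusive, so it can push events up into 'Related' and can inflate the treatment-related AE summary

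*Combined protocol and SAP*

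**What the plan says.** Section 10.3.1 asks the investigator first to judge whether a causal link is a reasonable possibility, and then to choose one of five labels.

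- **Related** has four alternatives joined by 'or'. The first two are "a known side effect of the study drug or there is a temporal relationship to the administration of the study drug"; the others are recurrence on rechallenge and abatement on dechallenge. Exclusion of another cause is not among them.
- **Probably Related** joins its conditions with 'and'. It opens with "When a reasonable temporal relationship exists between the adverse event and the study drug administration", adds "significant symptoms abate upon discontinuation of the study drug and there is a reasonable explanation based on known characteristics of the study drug", and also requires no clear association with other disease, therapy or factors.
- **Possibly Related** requires that the association is unknown but "the adverse event is not reasonably attributed to any other condition".
- **Unlikely Related** means little or no chance of a drug cause, with a competing cause most likely.
- **Not Related** means either no temporal relationship or an event clearly explained by another cause alone.

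The introductory list calls the second-lowest label 'probably not related', while the definition calls it 'Unlikely Related'. Section 10.2 speaks of 'definitely' related events, a label the scale does not contain.

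Section 13.3.1 uses the scale: "Adverse events will be summarized by maximum intensity (as described in Section 10.3.2) and relationship to study drug for each treatment group". It also plans a separate summary of treatment-related events, without saying which labels count.

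**The concern.** A causality scale should be harder to satisfy the further up one goes, and an event should have one place on it. Here timing alone meets the top label, while the next label down needs timing and three further conditions. The labels also overlap, and no tie-break is given. Section 10.3.3 shows that the authors knew how to write one, since it sets out a worst-case hierarchy for actions taken with study drug.

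The trial is open-label with no control group, and safety is part of the primary objective. Investigator attribution is therefore a main means of separating drug effects from transplant complications or relapse. If two investigators can apply the text faithfully and reach opposite labels, the by-relationship table and the treatment-related summary are hard to interpret.

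**Working it through.** The documents give no rate of adverse events or of related events, so there is no plan figure to reproduce. The check is logical: write each definition as a rule, list the possible event patterns, and count which rules each pattern meets.

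**Inputs (all from Section 10.3.1).** Four yes/no attributes: temporal relationship (T), known side effect or drug-based explanation (K), dechallenge (D), rechallenge (R). One three-level attribute: other cause (none, most likely, clearly the only one). Assumption: D and R can be 'yes' only if T is 'yes'.

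**Number of patterns.** With timing: 2 (K) × 2 (D) × 2 (R) × 3 (other cause) = 24. Without timing: 2 (K) × 3 (other cause) = 6. Total 24 + 6 = 30.

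| Label | Rule as coded | Patterns meeting it |
|---|---|---|
| Related | K or T or R or D | 24 + 3 = 27 |
| Probably | T and D and K and no other cause | 2 (R free) |
| Possibly | no other cause | 8 + 2 = 10 |
| Unlikely | other cause most likely or the only one | 16 + 4 = 20 |
| Not Related | no T, or other cause the only one | 6 + 8 = 14 |

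**Ordering.** Both 'Probably' patterns also meet 'Related', and 27 − 2 = 25 'Related' patterns do not meet 'Probably'. Nine patterns meet both 'Related' and 'Possibly' (8 with timing, 1 without). So 27 − 9 = 18 'Related' patterns fail 'Possibly', and only 10 − 9 = 1 'Possibly' pattern fails 'Related'. The top label is the widest of the three.

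**Overlap.** 'Related' and 'Not Related' are met together by 8 patterns (timing present, another cause the only one) + 3 (known effect, no timing) = 11. 'Related' and 'Unlikely' are met together by 16 + 2 = 18. 'Related' with either of the two is met by 18 + 1 = 19, the extra one being a known effect with neither timing nor another cause.

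**Shared cause.** The coding has no level for two equally plausible causes, so this case is reasoned from the text. Section 2.1.2 lists nausea and diarrhea among events reported with lenalidomide, and Appendix F stages gut GVHD by diarrhea volume or persistent nausea. Take on-drug diarrhea that either could explain. It is not 'Not Related', since the other cause is not the only one, and not 'Unlikely', since the chance of a drug cause is not small. If GVHD counts as a reasonable attribution, it fails 'Possibly'. If the GVHD association is clear, or dechallenge was not seen, it fails 'Probably'. 'Related' may then be the only label left.

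**Where the labels are used.**
1. The by-relationship table in 13.3.1 shows each label, so any upward shift appears there directly.
2. If the treatment-related summary pools possibly, probably and related, moves among those three leave the total unchanged. The total rises only through events that also fit 'Not' or 'Unlikely Related', or through shared-cause events that would otherwise have been kept out of 'Possibly'. If it counts 'Related' alone, the full shift enters.
3. In Section 4.3, the general DLT wording and items 1 to 5 do not use the five labels. Item 6 reads "Any treatment-related effect leading to a subject missing 3 or more doses of lenalidomide" and does not cite 10.3.1.
4. Section 10.4.1 says "Serious and unexpected AEs that are at least possibly related to the study drug must be reported to the FDA", so only serious, unexpected events are in play.

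**The case against.** Three stronger readings are tempting, and the documents do not carry them.

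**That nearly every event after the first dose will be 'Related', so the tables will be inflated.** No event rate supports this. Section 10.3.1 does not define a temporal relationship as anything after the first dose. The reasonable-possibility judgement comes before the labels, and 'Not Related' and 'Unlikely Related' apply just as literally as 'Related'. The text produces overlap without a tie-break, not automatic classification at the top. The counts above are patterns and cannot be read as proportions of events.

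**That Section 2.1.2 makes cytopenias, infections, nausea and diarrhea known side effects.** That section lists events whatever their presumed relationship to the drug, so listing alone does not meet that condition. A merely plausible other cause also does not necessarily defeat 'Possibly' or 'Probably'.

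**That dose escalation and expedited reporting rest on the same flawed scale.** Most of the DLT definition has its own attribution wording, and a link from item 6 to 10.3.1 is an inference. For FDA reporting, Section 10.1.2 defines unexpected against the Investigator Brochure, so the known-side-effect condition should rarely matter; the timing condition could. SAEs go to the drug supplier, the IRB and the DISC whatever their attribution.

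It is also fair that the trial is descriptive, and that the summaries of all AEs and all SAEs do not depend on attribution. These points limit the consequence. They leave the definitions as they are: a lower bar at the top, and no rule for overlap.

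**Conclusion.** The point holds for the definitions and, more narrowly, for their consequences. The scale is neither ordered nor mutually exclusive. Applied literally, it can push events up into 'Related' in the by-relationship table and can inflate the treatment-related summary, whose contributing labels are undefined. Compared with an ordered scale, the direction is upward. The size cannot be computed from the documents and depends on how far investigators' judgement overrides the wording.

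The effect on DLTs is confined to item 6, and only if that item is read through 10.3.1. The effect on FDA reporting is confined to serious, unexpected events. The counts rest on the coding shown, in particular that dechallenge and rechallenge presuppose timing. The main finding, that timing alone meets 'Related' but not 'Probably Related', needs no coding and can be read from the text. This is worth correcting because it is cheap and because attribution carries weight in an uncontrolled safety trial.

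**What to change.** Rewrite Section 10.3.1 as ordered, mutually exclusive categories:

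- 'Related' should need a temporal relationship **and** supporting evidence (known effect, dechallenge or rechallenge) **and** no more likely alternative cause.
- 'Possibly Related' should cover plausible timing with another cause also possible, so that shared-cause events have a place.
- State which category prevails if an event fits more than one.
- Use one name for the second-lowest label in place of 'probably not related' and 'Unlikely Related'.

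In Section 13.3.1, define treatment-related as possibly, probably or related.

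The cost is wording in these two sections and the key on the AE form. No extra data are needed.
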